## 8.9 Tables to present

### 8.9.1 Subject Disposition

**Table 3 Subject Disposition**

	Center1	Center2	Center3	.....	.....	Total
Screened						
Randomised						
Treatment  : NMES + EA and NMES+EA+SET						
Control  : EA and EA+SET						
Withdrawn						
Reason for withdrawal						
Completed						

### 8.9.2 Protocol Deviations

**Table 4 Listing of all Protocol Deviations**

Site	Subject ID	Type	Details of Deviation	Treatment	Start Date	End Date

**Table 5 Number of protocol deviations by centre and category**

Type of Deviation	Center1	Center2	Center3	.....	Total
Patient was incorrectly included in the trial (did not meet all the inclusion and exclusion criteria)	XX (XX.X%)				
.					
.					
Patient pregnancy	XX (XX.X%)				
Other	XX (XX.X%)				
Total					

**Table 6 Summary of Protocol Deviation of randomised patients (ITT) by treatment**

Variables	Treatment  : NMES + EA and NMES+EA+SET N=(XX)	Control  : EA and EA+SET N=(XX)	Total N=(XX)
Protocol Deviation or Violation			
Protocol Deviation	XX (XX.X%)	XX (XX.X%)	XX (XX.X%)
Protocol Violation	XX (XX.X%)	XX (XX.X%)	XX (XX.X%)
Type of Protocol Deviation			
Device administration	XX (XX.X%)	XX (XX.X%)	XX (XX.X%)
Sampling	XX (XX.X%)	XX (XX.X%)	XX (XX.X%)
Visit outside window	XX (XX.X%)	XX (XX.X%)	XX (XX.X%)
Other, please give details	XX (XX.X%)	XX (XX.X%)	XX (XX.X%)
Other			
Break in SET classes	XX (XX.X%)	XX (XX.X%)	XX (XX.X%)
Classes did not commence within 2 weeks of randomisation	XX (XX.X%)	XX (XX.X%)	XX (XX.X%)
Device not in use	XX (XX.X%)	XX (XX.X%)	XX (XX.X%)
Height and Weight not recorded	XX (XX.X%)	XX (XX.X%)	XX (XX.X%)
Non-SET class patient (we are a SET centre)	XX (XX.X%)	XX (XX.X%)	XX (XX.X%)
Peripheral pulses not assessed	XX (XX.X%)	XX (XX.X%)	XX (XX.X%)
Received wrong treatment - patient bought own device	XX (XX.X%)	XX (XX.X%)	XX (XX.X%)
Problems with attendance to SEP class	XX (XX.X%)	XX (XX.X%)	XX (XX.X%)
Treadmill not increased as per protocol could only increase to a maximum of 7.5% and not 8%	XX (XX.X%)	XX (XX.X%)	XX (XX.X%)
Incomplete data measurement at baseline	XX (XX.X%)	XX (XX.X%)	XX (XX.X%)
Any Protocol Deviation or Violation by site			
Cambridge University Hospital	XX (XX.X%)	XX (XX.X%)	XX (XX.X%)
Dorset County Hospital	XX (XX.X%)	XX (XX.X%)	XX (XX.X%)
Hull and East Yorkshire Hospitals	XX (XX.X%)	XX (XX.X%)	XX (XX.X%)
Imperial College Healthcare	XX (XX.X%)	XX (XX.X%)	XX (XX.X%)
Newcastle Upon Tyne Hospitals	XX (XX.X%)	XX (XX.X%)	XX (XX.X%)
North Bristol	XX (XX.X%)	XX (XX.X%)	XX (XX.X%)
Nottingham University Hospitals	XX (XX.X%)	XX (XX.X%)	XX (XX.X%)
Royal Bournemouth & Christchurch Hospital	XX (XX.X%)	XX (XX.X%)	XX (XX.X%)
St George's University Hospitals	XX (XX.X%)	XX (XX.X%)	XX (XX.X%)
Taunton & Somerset	XX (XX.X%)	XX (XX.X%)	XX (XX.X%)
University Hospital Southampton	XX (XX.X%)	XX (XX.X%)	XX (XX.X%)

 Treatment: NMES + Local Available Exercise Therapy (NMES+EA and NMES+EA+SET) Control: Local Available Exercise Therapy (EA and EA+SET)

### 8.9.3 Baseline Characteristics

**Table 7 Summary of baseline characteristics of randomised patients (ITT) by treatment**

Variable	Treatment  : NMES + EA and NMES+EA+SET N=(XX)	Control  : EA and EA+SET N=(XX)	Total N=(XX)
Age			
mean (SD)	XX.XX (XX.XX)	XX.XX (XX.XX)	XX.XX (XX.XX)
median (IQR)	XX.XX (XX.XX, XX.XX)	XX.XX (XX.XX, XX.XX)	XX.XX (XX.XX, XX.XX)
Sex N(%)			
Female	XX (XX.X%)	XX (XX.X%)	XX (XX.X%)
Male	XX (XX.X%)	XX (XX.X%)	XX (XX.X%)
Ethnicity N(%)			
Asian	XX (XX.X%)	XX (XX.X%)	XX (XX.X%)
Black	XX (XX.X%)	XX (XX.X%)	XX (XX.X%)
Mixed	XX (XX.X%)	XX (XX.X%)	XX (XX.X%)
White	XX (XX.X%)	XX (XX.X%)	XX (XX.X%)
Work status N(%)			
Higher managerial and professional occupations	XX (XX.X%)	XX (XX.X%)	XX (XX.X%)
Intermediate occupations (e.g. clerical, sales, service)	XX (XX.X%)	XX (XX.X%)	XX (XX.X%)
Lower managerial and professional occupations	XX (XX.X%)	XX (XX.X%)	XX (XX.X%)
Lower supervisory and technical occupations	XX (XX.X%)	XX (XX.X%)	XX (XX.X%)
Never worked or long-term unemployed	XX (XX.X%)	XX (XX.X%)	XX (XX.X%)
Routine occupations	XX (XX.X%)	XX (XX.X%)	XX (XX.X%)
Semi-routine occupations	XX (XX.X%)	XX (XX.X%)	XX (XX.X%)
Small employers and own account workers	XX (XX.X%)	XX (XX.X%)	XX (XX.X%)
Retired N(%)			
No	XX (XX.X%)	XX (XX.X%)	XX (XX.X%)
Yes	XX (XX.X%)	XX (XX.X%)	XX (XX.X%)
Performance limited due to IC (N%)			
A little	XX (XX.X%)	XX (XX.X%)	XX (XX.X%)
A lot	XX (XX.X%)	XX (XX.X%)	XX (XX.X%)
Not at all	XX (XX.X%)	XX (XX.X%)	XX (XX.X%)

 Treatment: NMES + Local Available Exercise Therapy (NMES+EA and NMES+EA+SET)

 Control: Local Available Exercise Therapy (EA and EA+SET)

Imperial Clinical Trials Unit	STATISTICAL ANALYSIS PLAN	NESIC
-------------------------------	---------------------------	-------

**Table 8 Summary of Medical History of randomised patients (ITT) by treatment**

Medical History	Treatment  : NMES + EA and NMES+EA+SET	Control  : EA and EA+SET	Total
	N(%)	N=(XX)	N=(XX)
Childbearing potential*			
No	XX (XX.X%)	XX (XX.X%)	XX (XX.X%)
Hypertension			
Yes	XX (XX.X%)	XX (XX.X%)	XX (XX.X%)
Stroke			
Yes	XX (XX.X%)	XX (XX.X%)	XX (XX.X%)
Heart attack			
Yes	XX (XX.X%)	XX (XX.X%)	XX (XX.X%)
High cholesterol			
Yes	XX (XX.X%)	XX (XX.X%)	XX (XX.X%)
Angina			
Yes	XX (XX.X%)	XX (XX.X%)	XX (XX.X%)
Diabetes			
Yes	XX (XX.X%)	XX (XX.X%)	XX (XX.X%)
Bypass revascularisation			
Yes	XX (XX.X%)	XX (XX.X%)	XX (XX.X%)
Angio revascularisation			
Yes	XX (XX.X%)	XX (XX.X%)	XX (XX.X%)
Other			
Yes	XX (XX.X%)	XX (XX.X%)	XX (XX.X%)

Data presented as frequency (percentage) for categorical variables

\*Female population only

Treatment: NMES + Local Available Exercise Therapy (NMES+EA and NMES+EA+SET)

Control: Local Available Exercise Therapy (EA and EA+SET)

**Table 9 Summary of Medication list of randomised patients (ITT) by treatment**

Concomitant Medications	Treatment  : NMES + EA and NMES+EA+SET	Control  : EA and EA+SET	Total
	N(%)	N=(XX)	N=(XX)
Antiplatelets			
Yes	XX (XX.X%)	XX (XX.X%)	XX (XX.X%)
Currently taking glycoprotein IIb IIIa antagonists			
Yes	XX (XX.X%)	XX (XX.X%)	XX (XX.X%)
Lipid modification therapy			
Yes	XX (XX.X%)	XX (XX.X%)	XX (XX.X%)
Anticoagulant			
Yes	XX (XX.X%)	XX (XX.X%)	XX (XX.X%)
Antihypertensives			
Yes	XX (XX.X%)	XX (XX.X%)	XX (XX.X%)
Other Medications			
Yes	XX (XX.X%)	XX (XX.X%)	XX (XX.X%)

Treatment: NMES + Local Available Exercise Therapy (NMES+EA and NMES+EA+SET)

Control: Local Available Exercise Therapy (EA and EA+SET)

Imperial Clinical Trials Unit	STATISTICAL ANALYSIS PLAN	NESIC
-------------------------------	---------------------------	-------

**Table 10 Summary of Vital Signs of randomised patients (ITT) by treatment**

Vital Signs	Treatment  : NMES + EA and NMES+EA+SET N=(XX)	Control  : EA and EA+SET N=(XX)	Total N=(XX)
Height			
mean (SD)	XX.XX (XX.XX)	XX.XX (XX.XX)	XX.XX (XX.XX)
median (IQR)	XX.XX (XX.XX, XX.XX)	XX.XX (XX.XX, XX.XX)	XX.XX (XX.XX, XX.XX)
Weight			
mean (SD)	XX.XX (XX.XX)	XX.XX (XX.XX)	XX.XX (XX.XX)
median (IQR)	XX.XX (XX.XX, XX.XX)	XX.XX (XX.XX, XX.XX)	XX.XX (XX.XX, XX.XX)
Pulse			
mean (SD)	XX.XX (XX.XX)	XX.XX (XX.XX)	XX.XX (XX.XX)
median (IQR)	XX.XX (XX.XX, XX.XX)	XX.XX (XX.XX, XX.XX)	XX.XX (XX.XX, XX.XX)
Systolic - Blood Pressure			
mean (SD)	XX.XX (XX.XX)	XX.XX (XX.XX)	XX.XX (XX.XX)
median (IQR)	XX.XX (XX.XX, XX.XX)	XX.XX (XX.XX, XX.XX)	XX.XX (XX.XX, XX.XX)
Diastolic - Blood Pressure			
mean (SD)	XX.XX (XX.XX)	XX.XX (XX.XX)	XX.XX (XX.XX)
median (IQR)	XX.XX (XX.XX, XX.XX)	XX.XX (XX.XX, XX.XX)	XX.XX (XX.XX, XX.XX)
BMI			
mean (SD)	XX.XX (XX.XX)	XX.XX (XX.XX)	XX.XX (XX.XX)
median (IQR)	XX.XX (XX.XX, XX.XX)	XX.XX (XX.XX, XX.XX)	XX.XX (XX.XX, XX.XX)

 Treatment: NMES + Local Available Exercise Therapy (NMES+EA and NMES+EA+SET)

 Control: Local Available Exercise Therapy (EA and EA+SET)

**Table 11 Summary of Lifestyle History of randomised patients (ITT) by treatment**

Lifestyle History	Treatment  : NMES + EA and NMES+EA+SET N=(XX)	Control  : EA and EA+SET N=(XX)	Total N=(XX)
Smoking status of subject N(%)			
Current smoker	XX (XX.X%)	XX (XX.X%)	XX (XX.X%)
Former smoker	XX (XX.X%)	XX (XX.X%)	XX (XX.X%)
Never	XX (XX.X%)	XX (XX.X%)	XX (XX.X%)
Current smoker (av. cigarettes/pipes per day)			
mean (SD)	XX.XX (XX.XX)	XX.XX (XX.XX)	XX.XX (XX.XX)
median (IQR)	XX.XX (XX.XX, XX.XX)	XX.XX (XX.XX, XX.XX)	XX.XX (XX.XX, XX.XX)
Former smoker (av. cigarettes/pipes per day)			
mean (SD)	XX.XX (XX.XX)	XX.XX (XX.XX)	XX.XX (XX.XX)
median (IQR)	XX.XX (XX.XX, XX.XX)	XX.XX (XX.XX, XX.XX)	XX.XX (XX.XX, XX.XX)
Electronic cigarettes N(%)			
No	XX (XX.X%)	XX (XX.X%)	XX (XX.X%)
Yes	XX (XX.X%)	XX (XX.X%)	XX (XX.X%)
Electronic cigarettes - Usage			
High user	XX (XX.X%)	XX (XX.X%)	XX (XX.X%)
Low user	XX (XX.X%)	XX (XX.X%)	XX (XX.X%)
Moderate user	XX (XX.X%)	XX (XX.X%)	XX (XX.X%)
Participant consume alcohol N(%)			
Current drinker	XX (XX.X%)	XX (XX.X%)	XX (XX.X%)
No	XX (XX.X%)	XX (XX.X%)	XX (XX.X%)
Current drinker (Number of units per week)			
mean (SD)	XX.XX (XX.XX)	XX.XX (XX.XX)	XX.XX (XX.XX)
median (IQR)	XX.XX (XX.XX, XX.XX)	XX.XX (XX.XX, XX.XX)	XX.XX (XX.XX, XX.XX)

 Treatment: NMES + Local Available Exercise Therapy (NMES+EA and NMES+EA+SET)

 Control: Local Available Exercise Therapy (EA and EA+SET)

**Table 12 Summary of Treadmill test of randomised patients (ITT) by treatment**

Treadmill Test	Treatment  : NMES + EA and NMES+EA+SET N=(XX)	Control  : EA and EA+SET N=(XX)	Total N=(XX)
Did the patient complete the treadmill test N(%)			
Yes	XX (XX.X%)	XX (XX.X%)	XX (XX.X%)
Patients subjective initial walking distance estimate			
mean (SD)	XX.XX (XX.XX)	XX.XX (XX.XX)	XX.XX (XX.XX)
median (IQR)	XX.XX (XX.XX, XX.XX)	XX.XX (XX.XX, XX.XX)	XX.XX (XX.XX, XX.XX)
Patients subjective absolute walking distance estimate			
mean (SD)	XX.XX (XX.XX)	XX.XX (XX.XX)	XX.XX (XX.XX)
median (IQR)	XX.XX (XX.XX, XX.XX)	XX.XX (XX.XX, XX.XX)	XX.XX (XX.XX, XX.XX)
Treadmill speed			
mean (SD)	XX.XX (XX.XX)	XX.XX (XX.XX)	XX.XX (XX.XX)
median (IQR)	XX.XX (XX.XX, XX.XX)	XX.XX (XX.XX, XX.XX)	XX.XX (XX.XX, XX.XX)
Incline			
mean (SD)	XX.XX (XX.XX)	XX.XX (XX.XX)	XX.XX (XX.XX)
median (IQR)	XX.XX (XX.XX, XX.XX)	XX.XX (XX.XX, XX.XX)	XX.XX (XX.XX, XX.XX)
Initial Claudication Distance ICD			
mean (SD)	XX.XX (XX.XX)	XX.XX (XX.XX)	XX.XX (XX.XX)
median (IQR)	XX.XX (XX.XX, XX.XX)	XX.XX (XX.XX, XX.XX)	XX.XX (XX.XX, XX.XX)
Absolute Walking Distance AWD			
mean (SD)	XX.XX (XX.XX)	XX.XX (XX.XX)	XX.XX (XX.XX)
median (IQR)	XX.XX (XX.XX, XX.XX)	XX.XX (XX.XX, XX.XX)	XX.XX (XX.XX, XX.XX)

Treatment: NMES + Local Available Exercise Therapy (NMES+EA and NMES+EA+SET)

Control: Local Available Exercise Therapy (EA and EA+SET)

#### 8.9.4 Derived Variables

**Table 13 Summary of ICQ and EQ-5D-5L - Quality of Life scores of randomised patients (ITT) by treatment**

QoL	Specific Score, mean(SD)	Treatment  : NMES + EA and NMES+EA+SET N=(XX)	Control  : EA and EA+SET N=(XX)	Total N=(XX)
ICQ*	ICQ health score			
	Baseline	XX.XX (XX.XX)	XX.XX (XX.XX)	XX.XX (XX.XX)
	12 weeks	XX.XX (XX.XX)	XX.XX (XX.XX)	XX.XX (XX.XX)
	6 months	XX.XX (XX.XX)	XX.XX (XX.XX)	XX.XX (XX.XX)
	12 months	XX.XX (XX.XX)	XX.XX (XX.XX)	XX.XX (XX.XX)
EQ-5D-5L	Health state score			
	Baseline	XX.XX (XX.XX)	XX.XX (XX.XX)	XX.XX (XX.XX)
	12 weeks	XX.XX (XX.XX)	XX.XX (XX.XX)	XX.XX (XX.XX)
	6 months	XX.XX (XX.XX)	XX.XX (XX.XX)	XX.XX (XX.XX)
	12 months	XX.XX (XX.XX)	XX.XX (XX.XX)	XX.XX (XX.XX)

\*The scores of ICQ where obtained using the procedure described in Appendix 2

Treatment: NMES + Local Available Exercise Therapy (NMES+EA and NMES+EA+SET)

Control: Local Available Exercise Therapy (EA and EA+SET)

**Table 14 Summary SF-36 of Quality of Life scores of randomised patients (ITT) by treatment**

QoL	Specific Score, mean (SD)	Treatment  : NMES + EA and NMES+EA+SET N=(XX)	Control  : EA and EA+SET N=(XX)	Total N=(XX)
		Section Score		
SF-36**				
Physical function				
Baseline		XX.XX (XX.XX)	XX.XX (XX.XX)	XX.XX (XX.XX)
12 weeks		XX.XX (XX.XX)	XX.XX (XX.XX)	XX.XX (XX.XX)
6 months		XX.XX (XX.XX)	XX.XX (XX.XX)	XX.XX (XX.XX)
12 months		XX.XX (XX.XX)	XX.XX (XX.XX)	XX.XX (XX.XX)
Role-Physical				
Baseline		XX.XX (XX.XX)	XX.XX (XX.XX)	XX.XX (XX.XX)
12 weeks		XX.XX (XX.XX)	XX.XX (XX.XX)	XX.XX (XX.XX)
6 months		XX.XX (XX.XX)	XX.XX (XX.XX)	XX.XX (XX.XX)
12 months		XX.XX (XX.XX)	XX.XX (XX.XX)	XX.XX (XX.XX)
Body pain				
Baseline		XX.XX (XX.XX)	XX.XX (XX.XX)	XX.XX (XX.XX)
12 weeks		XX.XX (XX.XX)	XX.XX (XX.XX)	XX.XX (XX.XX)
6 months		XX.XX (XX.XX)	XX.XX (XX.XX)	XX.XX (XX.XX)
12 months		XX.XX (XX.XX)	XX.XX (XX.XX)	XX.XX (XX.XX)
General Health				
Baseline		XX.XX (XX.XX)	XX.XX (XX.XX)	XX.XX (XX.XX)
12 weeks		XX.XX (XX.XX)	XX.XX (XX.XX)	XX.XX (XX.XX)
6 months		XX.XX (XX.XX)	XX.XX (XX.XX)	XX.XX (XX.XX)
12 months		XX.XX (XX.XX)	XX.XX (XX.XX)	XX.XX (XX.XX)
Vitality				
Baseline		XX.XX (XX.XX)	XX.XX (XX.XX)	XX.XX (XX.XX)
12 weeks		XX.XX (XX.XX)	XX.XX (XX.XX)	XX.XX (XX.XX)
6 months		XX.XX (XX.XX)	XX.XX (XX.XX)	XX.XX (XX.XX)
12 months		XX.XX (XX.XX)	XX.XX (XX.XX)	XX.XX (XX.XX)
Social functioning				
Baseline		XX.XX (XX.XX)	XX.XX (XX.XX)	XX.XX (XX.XX)
12 weeks		XX.XX (XX.XX)	XX.XX (XX.XX)	XX.XX (XX.XX)
6 months		XX.XX (XX.XX)	XX.XX (XX.XX)	XX.XX (XX.XX)
12 months		XX.XX (XX.XX)	XX.XX (XX.XX)	XX.XX (XX.XX)
Role-Emotional				
Baseline		XX.XX (XX.XX)	XX.XX (XX.XX)	XX.XX (XX.XX)
12 weeks		XX.XX (XX.XX)	XX.XX (XX.XX)	XX.XX (XX.XX)
6 months		XX.XX (XX.XX)	XX.XX (XX.XX)	XX.XX (XX.XX)
12 months		XX.XX (XX.XX)	XX.XX (XX.XX)	XX.XX (XX.XX)
Mental Health				
Baseline		XX.XX (XX.XX)	XX.XX (XX.XX)	XX.XX (XX.XX)
12 weeks		XX.XX (XX.XX)	XX.XX (XX.XX)	XX.XX (XX.XX)
6 months		XX.XX (XX.XX)	XX.XX (XX.XX)	XX.XX (XX.XX)
12 months		XX.XX (XX.XX)	XX.XX (XX.XX)	XX.XX (XX.XX)
Component Score				
Physical component score (PCS)				
Baseline		XX.XX (XX.XX)	XX.XX (XX.XX)	XX.XX (XX.XX)
12 weeks		XX.XX (XX.XX)	XX.XX (XX.XX)	XX.XX (XX.XX)
6 months		XX.XX (XX.XX)	XX.XX (XX.XX)	XX.XX (XX.XX)
12 months		XX.XX (XX.XX)	XX.XX (XX.XX)	XX.XX (XX.XX)
Mental component score (MCS)				
Baseline		XX.XX (XX.XX)	XX.XX (XX.XX)	XX.XX (XX.XX)
12 weeks		XX.XX (XX.XX)	XX.XX (XX.XX)	XX.XX (XX.XX)
6 months		XX.XX (XX.XX)	XX.XX (XX.XX)	XX.XX (XX.XX)
12 months		XX.XX (XX.XX)	XX.XX (XX.XX)	XX.XX (XX.XX)

 Treatment: NMES + Local Available Exercise Therapy (NMES+EA and NMES+EA+SET) Control: Local Available Exercise Therapy (EA and EA+SET)

\*\*The SF-36 scores were obtained using the procedure described in Appendix 2

Imperial Clinical Trials Unit	STATISTICAL ANALYSIS PLAN	NESIC
-------------------------------	---------------------------	-------

**Table 15 Summary of Compliance classification of randomised patients (ITT) by treatment**

Classification	Treatment  : NMES + EA and NMES+EA+SET N=(XX)	Control  : EA and EA+SET N=(XX)	Total N=(XX)
Compliance	XX (XX.X%)	XX (XX.X%)	XX (XX.X%)
Non-Compliance	XX (XX.X%)	XX (XX.X%)	XX (XX.X%)

Treatment: NMES + Local Available Exercise Therapy (NMES+EA and NMES+EA+SET)

Control: Local Available Exercise Therapy (EA and EA+SET)

### 8.9.5 Primary End Point Analysis

The primary end point will be analysed for the ITT population and PP population.

**Table 16 Summary of Absolute Walking Distance (AWD) by visit point and Treatment**

Visit	Treatment	N	Mean	SD	Median	Min	Max
Baseline							
	Treatment  : NMES + EA and NMES+EA+SET	XX	XX.XX	XX.XX	XX.XX	XX	XX
	Control  : EA and EA+SET	XX	XX.XX	XX.XX	XX.XX	XX	XX
3 months							
	Treatment  : NMES + EA and NMES+EA+SET	XX	XX.XX	XX.XX	XX.XX	XX	XX
	Control  : EA and EA+SET	XX	XX.XX	XX.XX	XX.XX	XX	XX
6 months							
	Treatment  : NMES + EA and NMES+EA+SET	XX	XX.XX	XX.XX	XX.XX	XX	XX
	Control  : EA and EA+SET	XX	XX.XX	XX.XX	XX.XX	XX	XX
12 months							
	Treatment  : NMES + EA and NMES+EA+SET	XX	XX.XX	XX.XX	XX.XX	XX	XX
	Control  : EA and EA+SET	XX	XX.XX	XX.XX	XX.XX	XX	XX

**Table 17 Tobit Regression Model for AWD at 3 months**

Variable	Coefficient	SE	t	P> t	Confidence interval
AWD(Baseline)	XX.XX	XX.XX	X.XX	X.XXX	X.XX
Treatment	XX.XX	XX.XX	X.XX	X.XXX	X.XX
Centre	XX.XX	XX.XX	X.XX	X.XXX	X.XX
Group	XX.XX	XX.XX	X.XX	X.XXX	X.XX
_cons	XX.XX	XX.XX	X.XX	X.XXX	X.XX
/sigma	XX.XX	XX.XX		X.XX	X.XX
Obs. Summary:	XX left-censored observations				
	XX uncensored observations				
	XX right-censored observations at (...) dependent variable				

Tobit Regression Model: AWD at 3 months = intercept + AWD (baseline) + Treatment +Centre + Group + residual error.

Treatment=NMES + local available Exercise therapy vs. local available Exercise therapy only (1,0), Group= Set or non-SET group (1,0) and Centre=centre identifier.

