### **8.3 Statistical analysis**

The primary analysis will estimate the mean difference in AWD between the two intervention arms using a linear regression model which will include intervention arm, baseline AWD, and the randomisation stratification variable 'centre' as covariates. A repeated measure analysis will be undertaken, including patient as a random effect, to investigate the relationship between AWD and independent

Imperial Clinical Trials Unit	NESIC Clinical Study Protocol V6.0 24/03/2020	Form Number CR001A-T
-------------------------------	---	-------------------------

baseline variables such as body mass index (BMI) with the model including adjustment for centre and baseline AWD. Multiple imputation will be undertaken for all participants who are missing values or drop out by three months. Causal inference methods will be used to estimate treatment effects that account for compliance with the allocated intervention (NMES, SET, EA). Where necessary, data will be transformed to meet normality assumptions. All statistical tests will be two-tailed with a 5% significance level.

Patient characteristics will be summarised. Summaries of continuous variables will be presented as means and standard deviations if normally distributed, and as medians and inter-quartile ranges for skewed data; categorical variables will be presented as frequencies and percentages. Data on the socioeconomic status of patients will be summarised by centre.

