### 5.7 Sample Size

Assuming that the mean AWD in the control group is 200m at 3 months [5] and a common equal standard deviation of 120m [6], without considering the dropout rate, it is estimated that a sample size of 172 participants (86 per group) will have 90% power with a two-sided alpha = 0.05 to detect a difference of 60m in the mean absolute walking distance at 3 months between the intervention and the control group.

Assuming a 10% dropout rate, the sample size required for this study is 192 participants; 96 in each arm.

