	
 
• Proportion of patients whose absolute walking distance at 3 months improved by 60 metres or more from baseline
 
• Proportions of patients whose absolute walking distance at 3 months improved by 100 metres or more from baseline
 
	Chi-square test at 3 months
	Investigate if NMES+EA has similar effect as SET+EA, at 3 months	Chi-square test at 3 months
	Subgroup analysis 4: NMES+EA vs SET +EA	Tobit Regression for absolute walking distance at 3 months with AWD at baseline, Treatment, Centre and Group as covariates.
	Proportion of patients whose absolute walking distance at 3 months improved by 60 metres or more from baseline	Chi-square test at 3 months
	Proportions of patients whose absolute walking distance at 3 months improved by 100 metres or more from baseline	Chi-square test at 3 months
	To determine if NMES+SET+EA is more effective than NMES+EA, at 3 months.	Tobit Regression for absolute walking distance at 3 months with AWD at baseline, Treatment, Centre and Group as covariates.
	Subgroup analysis 5: NMES+SET+EA vs NMES+EA	Chi-square test at 3 months
	Proportion of patients whose absolute walking distance at 3 months improved by 60 metres or more from baseline	Chi-square test at 3 months
	Proportions of patients whose absolute walking distance at 3 months improved by 100 metres or more from baseline	Chi-square test at 3 months

\*\*Primary outcome

T Mechanistic outcome

Summaries of continuous variables will be presented as mean and standard deviations if normally distributed, and as medians and inter-quartile ranges for skewed data. Categorical variables will be presented as frequencies and percentages in the form of summary tables.

All statistical tests will be two-tailed with a 5% significance level.

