**Table 64 Chi square test of Improvement of >60 m in AWD at three months between SET and Non-SET (subgroup1)**

Improvement of >60 m in the AWD at 3 months	NMES + Local available exercise therapy N=(XX)	Local available exercises therapy N=(XX)	Total	
			N=(XX)	N=(XX)
Yes	XX (XX.X%)	XX (XX.X%)	XX (XX.X%)	XX (XX.X%)
No	XX (XX.X%)	XX (XX.X%)	XX (XX.X%)	XX (XX.X%)

Imperial Clinical Trials Unit	STATISTICAL ANALYSIS PLAN	NESIC
-------------------------------	---------------------------	-------

**Table 65 Chi square test of Improvement of >100 m in AWD at three months between SET and Non-SET (subgroup1).** Same display as Table 64, but for improvement of >100 m in AWD and subgroup1.

**Table 66 Summary of AWD by Visit and for NMES+SET+EA vs SET+EA (subgroup2).** Same display as Table 62, but for subgroup2.

**Table 67 Output of Tobit Regression Model to assess the effects of NMES+SET + EA vs SET+ EA (subgroup2) for AWD at 3 months.** Same display as Table 63, but for subgroup2. Tobit Regression Model: AWD at 3 months = intercept + AWD (baseline)+ Treatment + Centre + Group + residual error. Treatment=NMES + local available Exercise therapy vs. local available Exercise therapy only (1,0), Centre=Centre identifier and Group= Set or non-SET group (1,0). Subgroup2: NMES+SET+EA vs SET+EA.

**Table 68 Chi square test of Improvement of >60 m in AWD at three months between NMES+SET + EA and SET+ EA (subgroup2).** Same display as Table 64, but for improvement of >100 m in AWD and subgroup2.

**Table 69 Chi square test of Improvement of >100 m in AWD at three months between NMES+SET + EA and SET+ EA (subgroup2).** Same display as Table 64, but for improvement of >100 m in AWD and subgroup2.

**Table 70 Summary of AWD by Visit and for NMES+EA vs EA (subgroup3).** Same display as Table 62, but for subgroup3.

**Table 71 Output of Tobit regression model to assess the effects of NMES+EA vs EA (subgroup3) for AWD at 3 months.** Same display as Table 63, but for subgroup3. Tobit Regression Model: AWD at 3 months = intercept + AWD (baseline)+ Treatment + Centre+ Group + residual error. Treatment=NMES + local available Exercise therapy vs. local available Exercise therapy only (1,0), Centre=Centre identifier and Group= Set or non-SET group (1,0). Subgroup3: NMES in the non-SET (NMES+EA vs EA).

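### The primary Tobit, as specified without a small-sample correction, tests at about 6% two-sided rather than the stated 5%

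*SAP*

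**What the plan says.** SAP 8.2 analyses 3-month AWD by Tobit regression, right-censored at 790 m. Table 17 writes it as "Tobit Regression Model: AWD at 3 months = intercept + AWD (baseline) + Treatment +Centre + Group + residual error". The table shell has rows for the constant and sigma, a t column and counts of censored observations, which is the usual layout of maximum-likelihood Tobit output.

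SAP 5.1 gives 11 centres. It adds that three SET centres later recruited exercise-only patients, so the group term can be estimated alongside centre. SAP 8.4 uses the same model for the subgroups.

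On error rate, SAP section 8 states: "All statistical tests will be two-tailed with a 5% significance level". Protocol 8.3 had planned a different method: "The primary analysis will estimate the mean difference in AWD between the two intervention arms using a linear regression model".

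Neither document states how the Tobit standard errors are obtained. Neither names a degrees-of-freedom correction, a bootstrap or a randomisation test.

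**The concern.** Maximum likelihood divides the residual sum of squares by n, whereas ordinary linear regression divides by n−k. The difference is negligible when k is small relative to n. Here k is 14 because of the centre indicators, against 172 evaluable patients.

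When almost nobody reaches the treadmill limit, the two methods give essentially the same treatment estimate. The Tobit nevertheless reports a smaller standard error without any extra information. At stake are the stated 5% level and the coverage of the 95% confidence interval for the single primary comparison, and for the subgroup models that have fewer patients per coefficient.

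**Working it through.** **Planning figure.** SAP 5.7 assumes "a common equal standard deviation of 120m" and 86 per group "to detect a difference of 60m in the mean absolute walking distance at 3 months". The two-sample t-test has power 0.8999 at 85 per arm and 0.9032 at 86, so 86 per arm (172) reproduces. With 10% dropout, 86/0.9 = 95.6, giving 96 per arm (192).

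**Expected censoring.** The SAP assumes "the mean AWD in the control group is 200m at 3 months", so the treated mean is 260 m.
- Control: (790 − 200)/120 = 4.92 SD, probability about 4 in 10 million.
- Treated: (790 − 260)/120 = 4.42 SD, probability about 5 in a million.

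At the planning values the Tobit is therefore in effect a normal regression with variance estimate RSS/n.

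**Coefficients.** Intercept 1 + baseline 1 + treatment 1 + centre 10 + group 1 = 14. Sigma is not counted.

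**Actual size.** The SE ratio is √((n−k)/n), and size = 2·P(t on n−k df > t₀.₉₇₅,ₙ₋ₖ × √((n−k)/n)). For the primary model the ratio is √(158/172) = 0.958. The critical value 1.975 acts as 1.975 × 0.958 = 1.893, and the two-sided tail of t on 158 df beyond 1.893 is 6.02%.

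| Model | n | k | SE ratio | Size |
|---|---|---|---|---|
| Primary, evaluable | 172 | 14 | 0.958 | 6.0% |
| Primary, all randomised | 192 | 14 | 0.963 | 5.9% |
| Primary, more missing (assumed) | 150 | 14 | 0.952 | 6.2% |
| Primary, centre as one numeric term | 172 | 5 | 0.985 | 5.3% |
| SET subgroup, 5 centres | 86 | 7 | 0.958 | 6.0% |
| SET subgroup, 6 centres | 86 | 8 | 0.952 | 6.2% |
| Non-SET subgroup, 9 centres | 86 | 11 | 0.934 | 6.7% |

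The subgroup n is an assumption: 96 planned per stratum (Protocol 3.2) less 10%. Group is constant within a stratum, so k = 3 + (centres − 1). Nine non-SET centres are the six exercise-only centres plus the three SET centres that also recruited such patients. Five or six SET centres are shown because SAP 5.1 says five and Protocol 4.1 lists six.

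**Simulation of the full Tobit** (12,000 null trials per scenario, centre-stratified allocation, Monte Carlo SE 0.2 points):
- Primary at the planning mean and SD: 6.1%.
- Primary with about 4% censored (assumed): 6.1%.
- Primary with about 12% censored (assumed): 5.9%.
- SET subgroup: 6.4%. Non-SET subgroup: 6.3%.

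A separate simulation at the planning values gave 5.9% uncorrected and 5.0% after scaling the covariance by n/(n−k). One at 15% censoring gave 5.4% uncorrected.

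**The case against.** **The SAP does not say what the standard errors are.** This is true. Maximum-likelihood standard errors are inferred from the method and from the layout of Table 17. It is the natural reading, and nothing in either document points elsewhere.

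**Table 17 prints a single Centre row.** Read as one numeric term, centre gives k = 5 and a size of 5.3%. The SAP calls it an indicator and an identifier, and a numeric score for 11 hospitals would have no meaning, so the factor reading is much the likelier.

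**The table already uses a t statistic.** That changes only the critical value, not sigma. The 6.02% already allows for t on 158 df; a normal reference would give 6.2%.

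**One percentage point is ordinary finite-sample behaviour.** This stands as a judgement on importance: only a p-value close to 0.05 would be affected. It is not a reason to leave the stated level undelivered when the remedy is so small.

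**Stronger readings that the documents do not support:**
- A reader might infer that the error favours the device. The tests are two-sided, so a small SE inflates both tails: about 3.0% each instead of 2.5%.
- A reader might infer that censoring makes matters worse. A 3,000-run simulation at 15% censoring did give 6.6%, but its 95% Monte Carlo interval is about 5.7 to 7.5%. The other runs gave 5.4% at 15% and 5.9% at 12%.
- A reader might extend the correction to subgroup analyses 4 and 5 (Tables 75 and 79). Under the SAP's coding, Treatment equals 1 − Group throughout subgroup 4, and every patient in subgroup 5 has Treatment = 1. No treatment coefficient can be estimated separately in either, so there is nothing to rescale.

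**Conclusion.** The point holds, at modest size. As written, the primary test has a true two-sided level of about 6% and a 95% confidence interval about 4% too narrow. The range is about 5.4 to 6% depending on censoring, and about 5.3% under the single-term reading of centre. The SET and non-SET subgroup models run at about 6.0–6.2% and 6.7% by formula; simulation did not separate them (6.4% and 6.3%).

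These figures assume uncorrected maximum-likelihood standard errors, centre as 10 indicators in the primary model, and normal errors with constant variance. The amount of censoring is not given in the documents. Multiple imputation was not part of the simulations above, but pooling does not itself rescale sigma.

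**What to change.** In SAP 8.2 and 8.4, and in the notes to Tables 17, 63, 67 and 71, state that the Tobit covariance matrix is multiplied by n/(n−k) and that tests and intervals use t on n−k degrees of freedom. Define k as the number of mean coefficients in the fitted model, with centre as a categorical factor. Table 63 has the same listed terms as Table 17; if the interaction described in SAP 8.4 is added, k rises by one.

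SAP 8.6.1 triggers multiple imputation when more than 5% of primary data are missing, and 10% dropout is planned. The sentence must therefore cover that case: apply the scaling within each imputed dataset before pooling, and use small-sample pooled degrees of freedom with n−k as the complete-data value.

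With no censored value, this reproduces the linear regression of Protocol 8.3. With censoring, it restores the 5% level approximately.

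The cost is a short SAP addition and a little code. Intervals widen by about 4% in the primary model (1/0.958 = 1.04) and about 7% in the non-SET subgroup (1/0.934 = 1.07). Design and data collection do not change.
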